6.2 Steps to Determine If an Adverse Event Requires Expedited Reporting

- Step 1: Identify the type of adverse event using the NCI Common Terminology Criteria for Adverse Events (CTCAE v4).
- Step 2: Grade the adverse event using the NCI CTCAE v4.

Step 3: Determine whether the adverse event is related to the protocol therapy Attribution categories are as follows:

- Definite The AE *is clearly related* to the study treatment.
- Probable The AE is likely related to the study treatment.
- Possible The AE *may be related* to the study treatment.
- Unrelated The AE is clearly NOT related to the study treatment.

Note: This includes all events that occur within 30 days of the last dose of protocol treatment. Any event that occurs more than 30 days after the last dose of treatment and is attributed (possibly, probably, or definitely) to the agent(s) must also be reported accordingly. SAEs and ECIs should be reported for 90 days after last pembrolizumab dose or until new anticancer treatment is initiated, but for a minimum of 30 days, whichever occurs first.

Step 4: Determine the prior experience of the adverse event.

Expected events are those that have been previously identified as resulting from administration of the agent. An adverse event is considered unexpected, for expedited reporting purposes only, when either the type of event or the severity of the event is not listed in the current known adverse events listed in:

- the current known adverse events listed this protocol;
- the drug package insert; and/or
- the current Investigator's Brochure

6.3 Data Collection Procedures for Adverse Events

The principal investigator is responsible for evaluating all adverse events, obtaining supporting documents, and determining that documentation of the event is adequate. He/she is responsible for determining the seriousness, severity, and relationship of the adverse event to the investigational drug. The principal investigator may delegate these duties to sub-investigators and must assure that these sub-investigators are qualified to perform these duties under the supervision of the principal investigator. All adverse events will be documented in the subject's source and recorded on Case Report Form(s).

The term of the adverse event should reflect the diagnosis rather than its symptoms, when available. In the event of death, the cause of death should be recorded as the adverse

IIT2015-18-[name]-MK3475

event. The detailed description of the event will include appropriately graded severity of the adverse event and its relationship to the study drug.

"Lack of efficacy" or "failure of expected pharmacological action" per se will not be reported as an AE or SAE. However, the signs and symptoms and/or clinical sequelae resulting from lack of efficacy will be reported if they fulfill the definition of an AE or SAE.

Events that **do not** meet the definition of an AE include:

Any clinically significant abnormal laboratory finding or other abnormal safety assessments that is associated with the underlying disease, unless judged by the investigator to be more severe than expected for the subject's condition.

Abnormal laboratory findings deemed by the investigator as not clinically significant.

The disease/disorder being studied, or expected progression, signs, or symptoms of the disease/disorder being studied, unless more severe than expected for the subject's condition

Medical or surgical procedure (e.g., endoscopy, appendectomy); the condition that leads to the procedure is an AE

Situations where an untoward medical occurrence did not occur (social and/or convenience admission to a hospital)

Anticipated day-to-day fluctuations of pre-existing disease(s) or condition(s) present or detected at the start of the study that do not worsen

All patients experiencing an adverse event will be monitored until:

- The adverse event resolves or the symptoms or signs that constitute the adverse event return to baseline:
- Any abnormal laboratory values have returned to baseline¹;
- There is a satisfactory explanation other than the study drug for the changes observed; or
- Death.

Serious adverse events, occurring after the informed consent is signed but prior to the initial dose of the investigational product will be collected as part of the subject's medical history/baseline symptoms but will only be reportable if they are considered by the Investigator to be causally related to required research procedures.

SAEs and ECIs should be reported for 90 days after last pembrolizumab dose or until new anticancer treatment is initiated, but for a minimum of 30 days, whichever occurs first.

If a laboratory abnormality is one component of a diagnosis or syndrome, then only the diagnosis or syndrome should be recorded on the AE page/screen of the eCRF. If the abnormality was not a part of a diagnosis or syndrome, then the laboratory abnormality should be recorded as the AE.

¹ An abnormal laboratory value is considered to be an AE if the abnormality: 1) results in discontinuation from the study; 2) requires treatment, modification/ interruption of IP dose, or any other therapeutic intervention; or 3) is judged to be of significant clinical importance. Regardless of severity grade, only laboratory abnormalities that fulfill a seriousness criterion need to be documented as a serious adverse event.

Non-serious adverse events (AEs) will be collected throughout the treatment period through the End of Treatment assessment 30 days after removal from treatment. Patients removed from treatment for unacceptable adverse events will be followed until resolution or stabilization of the adverse event. Events occurring during this period must be followed until resolution or death unless in the Investigator's opinion, the condition is unlikely to resolve due to the patient's underlying disease. After the End of Treatment assessment, any adverse event documented in the subject's medical record as being at least possibly related to study intervention will also be recorded in the Case Report Form.

SAEs must be reported to oversight agencies as described below.

6.4 Reporting Requirements for Adverse Events

6.4.1 Expedited Reporting to PI

The Principal Investigator must be notified within 24 hours of learning of any serious adverse events, regardless of attribution, occurring during the study or within 30 days of the last administration of the study drug. SAEs and ECIs should be reported for 90 days after last pembrolizumab dose or until new anticancer treatment is initiated, but for a minimum of 30 days, whichever occurs first.

Phone Number for Expedited Reporting: [contact]

Alternate Phone Number for Expedited Reporting: [contact]

6.4.2 Reporting to DSMC

Serious Adverse Event deemed to be related to the protocol and on-study deaths, including death of a research subject unless the death is expected (e.g. due to disease progression) to be reported to the DSMC within 24 hours for medical monitor ad hoc review between meetings to determine if immediate action is required. Reports may be emailed to the DSMC Admin at [contact].

6.4.3 Reporting to the Institutional Review Board (IRB)

The CSMC IRB requires that investigators report all adverse events that may represent an unanticipated problem involving risks to subjects or others as defined below.

All adverse events (those involving subjects who were enrolled at CSMC) which are both unexpected and probably related to the research must be reported to the IRB.

All reportable events should be submitted in CS-IRB to the Office of Research Compliance and Quality Improvement as **soon as possible**, **but no more than 10 days from the investigator's awareness of the event**.

The report must contain at least:

 Identification of the PI, study coordinator (if applicable), contact information, study title, and IRB number.

- A detailed summary of the problem, including all relevant details and the PI's assessment of the events leading up to the problem, to assist the IRB in its evaluation.
- A description of any action taken to address or remedy the problem, including a description of the resolution, if any, or current status.
- An assessment as to whether any changes are required in the conduct of the research to resolve the problem or prevent further problems.

6.4.4 Reporting to the Food and Drug Administration (FDA)

The investigator or his designee must submit documentation of adverse reactions according to the following reporting criteria:

- Reporting any unexpected fatal or life-threatening suspected adverse reactions no later than **7 calendar days** after initial receipt of the information
- Reporting any (1) serious, unexpected suspected adverse reactions, (2) findings from other clinical, animal, or in-vitro studies that suggest significant human risk, and (3) a clinically important increase in the rate of a serious suspected adverse reaction no later than 15 calendar days after determining that the information qualifies for reporting.

6.4.5 Expedited Reporting to Merck

All Adverse events will be documented according to GCP and graded according to CTCAE. **SAE** reports and any other relevant safety information are to be forwarded to the Merck Global Safety [contact].

Alternatively, reports may be called into the Merck National Service Center at [name], or sent via secure email to [contact].

A copy of all 15 Day Reports and Annual Progress Reports is submitted as required by FDA, European Union (EU), Pharmaceutical and Medical Devices agency (PMDA) or other local regulators. Investigators will cross reference this submission according to local regulations to the Merck Investigational Compound Number (IND, CSA, etc.) at the time of submission. Additionally, investigators will submit a copy of these reports to Merck & Co., Inc. (Attn: Worldwide Product Safety; [contact]) at the time of submission to FDA.

All subjects with serious adverse events must be followed up for outcome.

7.0 DRUG INFORMATION

7.1 Pembrolizumab

See current version of the Investigator's Brochure. Study drug will be provided by Merck.

The investigator shall take responsibility for and shall take all steps to maintain appropriate records and ensure appropriate supply, storage, handling, distribution and usage of investigational product in accordance with the protocol and any applicable laws and regulations. Clinical Supplies will be provided by Merck as summarized below:

Product Descriptions

Product Name & Potency	Dosage Form
pembrolizumab 100 mg/ 4mL	Solution for Injection

7.1.1 Packaging and Labeling Information

Clinical supplies will be affixed with a clinical label in accordance with regulatory requirements.

7.1.2 Clinical Supplies Disclosure

This trial is open-label; therefore, the subject, the trial site personnel, the Sponsor and/or designee are not blinded to treatment. Drug identity (name, strength) is included in the label text; random code/disclosure envelopes or lists are not provided.

7.1.3 Storage and Handling Requirements

Clinical supplies must be stored in a secure, limited-access location under the storage conditions specified on the label.

Receipt and dispensing of trial medication must be recorded by an authorized person at the trial site.

Clinical supplies may not be used for any purpose other than that stated in the protocol.

7.1.4 Returns and Reconciliation

The investigator is responsible for keeping accurate records of the clinical supplies received from Merck or designee, the amount dispensed to and returned by the subjects and the amount remaining at the conclusion of the trial.

Upon completion or termination of the study, all unused and/or partially used investigational product will be destroyed at the site per institutional policy. It is the Investigator's responsibility to arrange for disposal of all empty containers, provided that procedures for proper disposal have been established according to applicable federal, state, local and institutional guidelines and procedures, and provided that appropriate records of disposal are kept.

7.2 Olaparib

See current version of the package insert. Olaparib supply will be provided by Merck. Commercial supply will be used.

Olaparib will be provided as marketed packs of Lynparza (100 mg and 150 mg tablets in bottles of 120 tablets). Approved dosage is 300 mg (two 150 mg tablets) twice daily for a total daily dose of 600 mg daily. To manage adverse reactions, dose reduce to 250 mg (one 150 mg tablet and one 100 mg tablet) twice daily for a total daily dose of 500 mg. If further dose reduction is required, dose reduce to 200 mg (two 100 mg tablets) twice daily for a total daily dose of 400 mg.

8.0 CORRELATIVES/RESEARCH STUDIES

The main objective of the translational research component of the IIT is to obtain biomarker measurements of PD-1 and PD-L1 expressions. Archival tumor samples will be sent to Qualtek Molecular Laboratories for analysis. See Sample Handling Manual.

9.0 STATISTICAL CONSIDERATIONS

Therapy administered until documented/confirmed progression by RECIST 1.1 criteria. This trial is a pilot study to assess the objective response rate with immunotherapy and PARP inhibition.

There are no preliminary statistical assumptions. First response assessments at 9 weeks; time interval for trial assessment is typical for time interval for assessment of response to standard of care therapy. Investigational therapy will not preclude subsequent standard of care therapy or subsequent investigational therapy.

9.1 Study Design/Study Endpoints

This study is a pilot study intended to determine ORR to single agent pembrolizumab in addition to standard of care olaparib treatment in study population.

9.2 Sample Size and Early Stopping

Clinical benefit is defined as complete response, partial response, or stable disease (if stable disease, lasting for at least four months). A proportion of patients with clinical benefit less than 15% will be of no interest. The new treatment would be of interest if the proportion of patients with clinical benefit is at least 41%. Simon's two-stage design (Simon, 1989) will be used. The null hypothesis: p<= 0.15 is against the alternative hypothesis p>= 0.41. In the first stage, 10 patients will be accrued. If there are 2 or fewer subjects with clinical benefit among these 10 patients, the study will be terminated. The probability of early stopping under the null is 0.82, and under the alternative is 0.16. Otherwise, 10 additional patients will be accrued for a total of 20. The null hypothesis will be rejected if 6 or more responses are observed in 20 patients. This design yields a 1-sided type I error rate of 5% and power of 80%.

The early stopping rule is based on responses in the first 10 patients, rather than dose limiting toxicity, as the study drug is FDA-approved at the current dose used in this trial, has a known and predictable rate of toxicity at the present dose, has been used in prior cohorts of breast cancer patients at the current dose, and there is no biological basis on which to expect excessive or unusual toxicity in the study cohort.

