1.0 BACKGROUND AND RATIONALE

1.1 Disease Background

Breast cancer due to germline BRCA 1 or BRCA2 mutation represents approximately 5-10% of the breast cancer population. BRCA 1 and 2 germline mutations are readily determined through commercially available testing of blood and buccal cell DNA. While all breast cancer molecular subtypes may occur in BRCA mutation carriers, it is recognized that approximately 70% of breast cancers developing in BRCA 1 carriers are likely to be triple negative, while over 50% of breast cancer developing in BRCA 2 carriers are estrogen receptor positive. HER2 positive breast cancers may also occur with either BRCA 1 or BRCA2 mutations at a frequency of 10-13% [1]. Historically, breast cancer in BRCA mutation carriers has not been treated differently than breast cancer occurring "sporadically", according to standard of care guidelines [2, 3]. An inhibitor of the poly (ADP) ribose polymerase (PARP) 1 enzyme, olaparib[4], has been FDA-approved for use in BRCA-mutated ovarian cancer, and clinical trials were recently conducted with these compounds in breast cancer [5]. In 2018, the FDA approved olaparib for germline BRCA-mutated metastatic breast cancer [21]. Response rates with PARP inhibitors in BRCA-mutated breast cancer have ranged from 0 to 41%, with a median progression free survival of 6 months [6, 7]. There remains a significant unmet need for therapy with specific benefit in BRCA-mutated breast cancer. Immunotherapy may offer a targeted therapy with less toxicity than chemotherapy, and potentially greater efficacy for this population with an unmet need for targeted therapy approaches. Positive results in this cohort would be of major clinical research interest and benefit to this population.

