2.0 STUDY OBJECTIVES

2.1 Primary Objective

Overall Response Rate (ORR) of pembrolizumab therapy in addition to olaparib therapy in advanced BRCA-mutated or HDR-defect breast cancer, as measured by RECIST 1.1, in patients progressing after prior therapy.

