2.4 Endpoints

Therapy administered until documented progression by RECIST 1.1 criteria or unacceptable toxicity.

This trial is a pilot study to assess the objective response rate with immunotherapy. There are no preliminary statistical assumptions. Stopping rules described in Section 9.

First response assessments at 9 weeks; time interval for trial assessment is typical for time interval for assessment of response to standard of care therapy. Investigational therapy will not preclude subsequent standard of care therapy or subsequent investigational therapy.

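### Section 9.2 tests against an unsourced 15% null although every patient takes olaparib, and switches endpoint between stages; on either reading, rejection would not show activity beyond olaparib

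*Combined protocol and SAP*

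**What the plan says.** Section 9.2 defines clinical benefit as CR, PR, or SD lasting at least four months. It then sets the null: "A proportion of patients with clinical benefit less than 15% will be of no interest". A rate of 41% or more would be of interest. Neither figure has a source.

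The stage 1 rule is written for clinical benefit: "If there are 2 or fewer subjects with clinical benefit among these 10 patients, the study will be terminated". The final rule uses another word: "The null hypothesis will be rejected if 6 or more responses are observed in 20 patients". The second paragraph of 9.2 uses that word for stage 1 as well: "The early stopping rule is based on responses in the first 10 patients". Section 9.2 states a one-sided type I error of 5%, power of 80%, and early-stopping probabilities of 0.82 (null) and 0.16 (alternative).

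The primary objective in section 2.1 is "Overall Response Rate (ORR) of pembrolizumab therapy in addition to olaparib therapy", and section 9.1 also names ORR. Section 2.4 says: "This trial is a pilot study to assess the objective response rate with immunotherapy". The parallel sentence in section 9.0 adds PARP inhibition.

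Under section 4.1 the trial has a single arm and all patients take olaparib. The only PARP-inhibitor benchmark is in section 1.1: "Response rates with PARP inhibitors in BRCA-mutated breast cancer have ranged from 0 to 41%, with a median progression free survival of 6 months". Patients with prior PARP-inhibitor exposure are eligible (sections 1.1 and 3.2.5.1), as are patients with HDR-defect tumours.

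**The concern.** The 5% error rate protects against a false claim only when the true rate is 15% or less. Olaparib is active in this disease by the protocol's own account, so the rate without any pembrolizumab effect may be well above 15%. A regimen no better than olaparib could then pass the futility look and reject the null.

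The change of endpoint adds to this. If the final rule counts clinical benefit, the null has to be judged against clinical benefit on olaparib. If it counts CR+PR, the null has to be judged against the response range in section 1.1, and the two stages no longer test the same quantity, so the stated error rate does not follow.

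At stake is what a positive result may be said to show. No passage says that rejection leaves the contribution of pembrolizumab unknown.

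**Working it through.** **1. Reproduce the plan.** Inputs from section 9.2: 10 patients in stage 1, stop at 2 or fewer; 20 in total, reject at 6 or more; null 0.15, alternative 0.41. With one endpoint at both stages and true rate p:

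- P(early stop) = P(X₁ ≤ 2), with X₁ ~ Bin(10, p).
- P(reject) = Σ over x = 3 to 10 of P(X₁ = x) · P(X₂ ≥ 6 − x), with X₂ ~ Bin(10, p).

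At p = 0.15, P(early stop) = 0.1969 + 0.3474 + 0.2759 = 0.820. P(reject) = 0.1298·0.1798 + 0.0401·0.4557 + 0.0085·0.8031 + 0.0013 ≈ 0.0498. At p = 0.41 the results are 0.152 and 0.806. The stated 5%, 80% and 0.82 reproduce; 0.16 is within one point. A plain rule of 6 or more of 20 with no interim look would give 0.067 and 0.892, so the stated figures need the same endpoint at both looks.

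**2. What section 1.1 could imply for olaparib alone.** All patients have measurable disease (section 3.1.4), so a patient alive and progression-free at 4 months is CR, PR, or SD of at least 4 months, if SD duration runs from treatment start (assumed).

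- With a 6-month median PFS, S(4) ≥ S(6) = 0.50, whatever the shape of the curve.
- If PFS is exponential, S(4) = 0.5^(4/6) = 0.63.

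This is an approximation. A PFS curve censors early dropouts, whereas section 4.8 replaces patients with under 6 weeks of treatment. It also assumes that the quoted median describes the patients enrolled.

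**3. Clinical benefit at both stages, pembrolizumab adding nothing.** All rates are assumptions.

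| Olaparib-alone rate | P(reject) | P(early stop) |
|---|---|---|
| 25% | 30% | 53% |
| 35% | 65% | 26% |
| 45% | 88% | 10% |
| 50% | 94% | 5.5% |
| 63% | 99% | 0.7% |

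The 25% row is what results if half the patients have a 0% rate and half have 50%: 0.5·0 + 0.5·0.50 = 0.25.

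**4. Clinical benefit at stage 1, CR+PR at the end.** Let c be the true clinical benefit rate and q the true CR+PR rate, with responders a subset of those with benefit. Stage 1 is trinomial (probabilities q, c − q, 1 − c). The trial continues if more than 2 of 10 have benefit and rejects if CR+PR totals 6 or more of 20.

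| q | P(reject), c = 0.50 | P(reject), c = 0.63 |
|---|---|---|
| 15% | 6.7% | 6.7% |
| 20% | 19% | 20% |
| 25% | 38% | 38% |
| 30% | 57% | 58% |
| 41% | 86% | 89% |

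At q = 15% this is the type I error of the final test: 6.7%, not 5%. The futility look hardly ever stops the trial, so it no longer reduces the error rate. If CR+PR is counted at both stages, the 5% holds, and a 41% response rate on olaparib alone would reject 80.6% of the time (step 1).

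**5. What the data could show.** Exact (Clopper-Pearson) 95% intervals, not adjusted for the two stages: 6/20 gives 12 to 54%; 14/20 gives 46 to 88%; 15/20 gives 51 to 91%; 18/20 gives 68 to 99%. Every result from 6 to 14 of 20 rejects the 15% null with an interval that includes 50%.

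**The case against.** The strongest objection is to the benchmark. Section 1.1 gives no clinical benefit rate. It quotes one median PFS beside a response range of 0 to 41%, and a single median need not describe both ends of that range. A reader might infer that section 1.1 establishes a rate of 50% or more on olaparib alone, so that rejection is nearly certain. The documents do not support that. Pretreated patients are eligible with no stated share or response rate, and a plausible mix brings the rate to about 25%, where the rule rejects 30% of the time and stops early 53% of the time. This part of the objection stands, so the 50% and 63% figures are assumptions. For HDR-defect tumours, however, section 1.2.2 claims the same propensity to PARP-inhibitor sensitivity as for BRCA-mutated ones, so the documents give no ground for a lower rate there.

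A second stronger reading is that the plan claims to isolate pembrolizumab. It does not say so. Section 9.0 describes the target as the regimen, this is a single-arm pilot, and sections 2.4 and 9.0 disclaim preliminary statistical assumptions. That also stands. But 9.2 runs a formal test with stated error rates, and 9.1 frames the aim as pembrolizumab added to olaparib, so a sentence limiting the conclusion is needed.

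Third, the final rule may mean CR+PR. The benchmark derived from PFS then does not apply to the final test. The 15% null still lies inside the 0 to 41% range, and the 41% target equals its upper end.

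**Conclusion.** The concern holds in limited form. The arithmetic of 9.2 is sound for one endpoint used at both stages. Its 15% null has no source and takes no visible account of olaparib, and the endpoint of the final rule is not fixed.

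On the clinical-benefit reading, a regimen no better than olaparib would reject with probability from 30% to 99% over assumed olaparib-alone rates of 25% to 63%; the figure depends on an enrolment mix the documents do not give. On the CR+PR reading with stage 1 on clinical benefit, the type I error is about 6.7% if true clinical benefit is 50 to 63%, and rejection does not separate the combination from the upper part of the range in section 1.1. On neither reading does rejection show activity beyond olaparib.

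This should be fixed, with moderate confidence. The endpoint switch can be read directly from the text; the size of the null problem rests on the assumptions above.

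**What to change.** Keep 20 patients and the current cut-offs.

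- **Section 9.2, endpoint.** Name one endpoint and use it in the hypotheses, the stage 1 rule and the final rule. Reconcile it with the ORR primary objective in section 2.1. This restores the stated 5%.
- **Sections 9.1 and 9.2, interpretation.** State that rejecting the null shows only that the rate on this endpoint exceeds 15% for the regimen, and does not show activity beyond olaparib alone or a contribution of pembrolizumab.
- **Section 9.2, operating characteristics.** Next to the 5%, report P(reject) and P(early stop) at olaparib-alone rates of 25%, 35%, 45%, 50% and 63% (the table in step 3), labelled as assumptions.
- **Section 9.3, reporting.** Give the final rate with an exact 95% CI. Read it descriptively against section 1.1: 0 to 41% for ORR or, for clinical benefit, an assumed range derived from the median PFS. Add a descriptive split by prior PARP-inhibitor exposure; the intervals will be wide.

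The cost is wording, one small table, one interval and one split. The downside is that the permitted claim and the stated operating characteristics become less favourable.

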2.2 Secondary Objectives

- **2.2.1** Progression Free Survival (PFS), as measured by RECIST 1.1, in patients progressing after prior therapy from baseline to the date of the first evidence of progression for up to two years.
- **2.2.2** Overall survival (OS), from baseline until death for up to two years.
- **2.2.3** Clinical Benefit Rate (CR+PR+SD), as measured by RECIST 1.1, in patients progressing after prior therapy from baseline for up to two years.
- **2.2.4** Duration of Response (DOR) for CR and PR, as measured by RECIST 1.1, in patients progressing after prior therapy from baseline for up to two years.

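### The primary objective is ORR, but the two-stage test in 9.2 is set on clinical benefit, its final rule counts undefined responses, and no section states how the roles are split

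*Combined protocol and SAP*

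**What the plan says.** Four places make response rate the trial's question. Section 2.1 gives the primary objective as "Overall Response Rate (ORR) of pembrolizumab therapy in addition to olaparib therapy". Section 2.4 says "This trial is a pilot study to assess the objective response rate with immunotherapy. There are no preliminary statistical assumptions". Section 9.0 says "This trial is a pilot study to assess the objective response rate with immunotherapy and PARP inhibition" and repeats that "There are no preliminary statistical assumptions". Section 9.1 says "This study is a pilot study intended to determine ORR".

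Clinical benefit is a secondary objective in 2.2.3: "Clinical Benefit Rate (CR+PR+SD), as measured by RECIST 1.1", with no minimum duration for stable disease.

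Section 9.2 defines clinical benefit more narrowly (CR, PR, or SD of four months or more). It calls a rate below 15% uninteresting and gives the rate of interest as "The new treatment would be of interest if the proportion of patients with clinical benefit is at least 41" percent. It stops the trial if 2 or fewer of the first 10 patients have clinical benefit. The final rule changes the word: "The null hypothesis will be rejected if 6 or more responses are observed in 20 patients". A one-sided 5% type I error and 80% power are claimed for the whole design. The next paragraph of 9.2 describes the same stage 1 rule as resting on responses.

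Section 9.3 names no estimate or interval for ORR. Section 4.8 makes patients with less than 6 weeks of treatment non-evaluable for efficacy and replaces them.

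**The concern.** The only formal test in the plan is not a test of the primary objective, and nothing says that this is intended. Estimating ORR while basing go/no-go on clinical benefit is a permissible design, but it has to be stated. Otherwise a rejection driven by stable disease could be taken as a positive response-rate result.

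The change of word in the final rule adds a second difficulty. Section 2.2.4 ties duration of response to CR and PR, so an analyst working from the primary objective could count only CR and PR at the end. The same 20 patients could then give two different verdicts. The trial is open-label, so the choice could be made with outcomes in view.

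**Working it through.** **Inputs (9.2).** n1 = 10, stop at 2 or fewer; n = 20, reject at 6 or more; p0 = 0.15, p1 = 0.41. Below, b(n,x,p) is the binomial probability, c the true clinical benefit rate and o the true ORR, with CR+PR nested in clinical benefit. All (o, c) pairs are assumptions.

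**1. The plan's own figures, one endpoint at both stages.**

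P(stop) = P(Bin(10,p) ≤ 2):
- p = 0.15: 0.1969 + 0.3474 + 0.2759 = 0.820 (stated 0.82).
- p = 0.41: 0.0051 + 0.0355 + 0.1111 = 0.152 (stated 0.16, an immaterial difference).

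P(reject) = Σ over x = 3..10 of b(10,x,p) × P(Bin(10,p) ≥ 6 − x):
- p = 0.15: 0.12983×0.1798 + 0.0401×0.4557 + 0.00849×0.8031 + 0.0014 = 0.0498.
- p = 0.41: 0.20582×0.8483 + 0.2503×0.9594 + 0.20873×0.9949 + 0.1834 = 0.806.

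So 5% and 80% are reproduced. A cut-off of 5 gives alpha 0.101 and a cut-off of 7 gives power 0.728, so only 6 fits both figures.

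**2. What that test says about ORR.** On this reading P(reject) depends on c alone: 0.05, 0.48 and 0.81 at c = 15%, 30% and 41%. Those values hold even if ORR is 15% in all three cases. This is the power curve for clinical benefit, not an error rate for ORR.

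**3. Final count on CR+PR, stage 1 on clinical benefit.**

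P(reject) = Σ over x = 3..10 of b(10,x,c) × Σ over y = 0..x of b(x,y,o/c) × P(Bin(10,o) ≥ 6 − y).

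| Clinical benefit | ORR | P(reject) |
|---|---|---|
| 41% | 41% | 0.806 |
| 41% | 35% | 0.700 |
| 41% | 30% | 0.551 |
| 41% | 25% | 0.367 |
| 41% | 20% | 0.190 |
| 15% | 15% | 0.0498 |
| 15% | 10% | 0.009 |
| 25% | 15% | 0.060 |
| 30% | 15% | 0.062 |
| 41% | 15% | 0.066 |
| 60% | 15% | 0.067 |

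At 41% clinical benefit the power of 80% is kept only if none of the benefit is stable disease. If the null is read as ORR 15%, the 5% is exceeded once clinical benefit is higher than ORR.

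Six or more CR+PR implies six or more with clinical benefit. The chance that the two counts give opposite verdicts is therefore the difference in P(reject). At c = 41%: 0.806 − 0.700 = 0.11, 0.806 − 0.551 = 0.25, 0.806 − 0.367 = 0.44 and 0.806 − 0.190 = 0.62, at ORR 35%, 30%, 25% and 20%.

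**4. Which reading the text favours.** For clinical benefit: 9.2 tests a single p, defined on clinical benefit; its second paragraph uses responses for the clinical benefit stopping rule; and the version 5 change log treats favorable response and clinical benefit as one term, though only for early stopping. Against: 2.2.4 ties response to CR and PR, and Section 1.1 quotes PARP-inhibitor response rates of 0 to 41%, whose upper end equals p1. The documents do not link the two figures.

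**5. ORR as an estimate.** Clopper-Pearson 95% limits are the 0.025 quantile of Beta(k, n−k+1) and the 0.975 quantile of Beta(k+1, n−k):
- 4/20: 0.057 to 0.437.
- 1/10: 0.0025 to 0.445.

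The mean ORR estimate given that stage 1 is passed is [(o/c) × E(X1 | X1 ≥ 3) + 10o]/20, where X1 is the stage 1 clinical benefit count. For o = c = 0.15, E(X1 | X1 ≥ 3) = (1.5 − 0.3474 − 2×0.2759)/0.1798 = 3.34, so the mean is (3.34 + 1.5)/20 = 0.242, which is 9 points too high. For (o, c) = (0.10, 0.15), (0.15, 0.30), (0.30, 0.41) and (0.20, 0.41) the means are 0.161, 0.173, 0.316 and 0.210, which are 6, 2, 2 and 1 points too high.

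**The case against.** The strongest reply is that nothing in the design is miscalculated. Section 9.2 defines clinical benefit, sets both rates and the stage 1 rule on it, and the 5% and 80% reproduce. On that view the defect is one loose word and a missing sentence, in a single-arm pilot of 20. Most of this stands. It is why the point does not challenge the sample size or cut-offs.

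A reader might infer from the second table that the trial's real power is 19% to 70%, or that its type I error is above 5%. The documents do not support that. Those figures need the less likely reading of the final rule and response rates that the plan does not give. Likewise, no section says that a rejection will be reported as a response-rate result; the risk is that nothing prevents it.

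The match between p1 and the 41% in Section 1.1 works in the other direction. It does not prove that p1 began as a response rate, but it means that the intended endpoint should be confirmed with the sponsor and not assumed.

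What remains is that a plan with a formal rejection rule must say what is counted, and the label of pilot does not remove that need.

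**Conclusion.** The concern holds as a matter that should be fixed, not as a fatal error. ORR is the primary objective, yet the only hypotheses and error rates belong to clinical benefit, and the final count is not defined. With clinical benefit at both stages the type I error is 0.0498 and the power 0.806, for clinical benefit only. With CR+PR as the final count, P(reject) at 41% clinical benefit falls to between 0.70 and 0.19 for ORR 35% to 20%, and at ORR 15% it is 0.060 to 0.067 for clinical benefit of 25% to 60%. The first pair of figures rests on the documents alone; the rest depend on assumed rates.

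Two smaller contradictions belong with this. Stable disease has no minimum duration in 2.2.3 but needs four months in 9.2. The denial of statistical assumptions in 2.4 and 9.0 conflicts with the rates and error levels in 9.2, although it changes no decision.

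**What to change.** 1. In 9.2, use one named endpoint in the final rule and in the early stopping paragraph. As p0, p1 and stage 1 are written for clinical benefit, the direct change is to count subjects with clinical benefit, and to say that the 5%, the 80% and the go/no-go decision refer to that endpoint. The sponsor should first confirm that 15% and 41% were meant for clinical benefit. If they were meant for ORR, both stages must be restated for ORR, which is a design change and not a clarification.
2. Keep ORR as the primary objective and say that it is estimated with an exact 95% confidence interval, both at 20 patients and if the trial stops at 10. Say that the interval is not adjusted for stage 1 selection, state the denominator in view of the replacement rule in 4.8, and state that rejecting the null is not a claim about ORR.
3. Make the stable disease requirement in 2.2.3 match 9.2, and remove the statement in 2.4 and 9.0 that there are no statistical assumptions.
4. Record whether the change was made before or after any review of outcome data. The text is version 9 of December 2023, the trial is open-label, and enrolment status is not given.

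If clinical benefit is confirmed, the cost is a wording amendment; the sample size, cut-offs and procedures stay. The downside is that ORR carries no formal test, and its estimate after passing stage 1 is biased upward, by about 1 to 9 points in the cases computed. With 20 patients the interval is also wide (6% to 44% at 4/20).
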